8.2 DATA QUALITY ASSURANCE

A risk-based approach is used for study quality management. It is initiated by the assessment of critical data and processes for study subject protection and reliability of the results as well as identification and assessment of associated risks. An Integrated Quality and Risk Management Plan or alternative plan, in line with the guidance provided by ICH Q9 and ICH-GCP E6, for fully outsourced studys, documents the rationale and strategies for risk management during study conduct including monitoring approaches, vendor management and other processes focusing on areas of greatest risk.

Continuous risk review and assessment may lead to adjustments in study conduct, study design or monitoring approaches.

A quality assurance audit / inspection of this study may be conducted by the contracting entity, contracting entity's designees, or by IRB / IEC or by regulatory authorities. The quality assurance auditor will have access to all medical records, the investigator's study-related files and correspondence, and the informed consent documentation of this study.

8.3 RECORDS

CRFs for individual patients will be provided by the contracting entity.

8.3.1 Source documents

In accordance with regulatory requirements, the investigator should prepare and maintain adequate and accurate source documents and study records that include all observations and other data pertinent to the investigation on each study patient. Source data as well as reported data should follow the "ALCOA principles" and be **a**ttributable, **l**egible, **c**ontemporaneous, **o**riginal and **a**ccurate. Changes to the data should be traceable (audit trail).

Data reported on the CRF must be consistent with the source data or the discrepancies must be explained.

The current medical history of the patient may not be sufficient to confirm eligibility for the study and the investigator may need to request previous medical histories and evidence of any diagnostic tests. In this case, the investigator must make at least one documented attempt to retrieve previous medical records. If this fails, a verbal history from the patient, documented in their medical records, would be acceptable.

Before sending or uploading those copies, the investigator must ensure that all patient identifiers (e.g. patient's name, initials, address, phone number, social security number) have properly been removed or redacted from any copy of the patients' source documents. If the patient is not compliant with the protocol, any corrective action e.g. re-training must be

documented in the patient file.

For the CRF, data must be derived from source documents, for example:

• Patient identification: gender, year of birth (in accordance with local laws and regulations)

Proprietary confidential information © 2022 Boehringer Ingelheim International GmbH or one or more of its affiliated companies

- Patient participation in the study (substance, study number, patient number, date patient was informed)
- Dates of patient's visits.
- Medical history (including study indication and concomitant diseases, if applicable)
- Medication history
- Adverse events and outcome events (onset date (mandatory), and end date (if available))
- Serious adverse events (onset date (mandatory), and end date (if available))
- Concomitant therapy (start date, changes)
- Originals or copies of laboratory results and other imaging or testing results, with proper documented medical evaluation (in validated electronic format, if available)
- Completion of patient's participation in the study (end date; in case of premature discontinuation document the reason for it).
- Prior to enrolment of a patient to this study, there must be documented evidence in the source data (e.g. medical records) that the study participant meets all inclusion criteria and does not meet any exclusion criteria. The absence of records (either medical records, verbal documented feedback of the patient or testing conducted specific for a protocol) to support inclusion / exclusion criteria does not make the patient eligible for the study.

8.3.2 Direct access to source data and documents

The investigator / institution will allow site study-related monitoring, audits, IRB / IEC review and regulatory inspections. Direct access must be provided to the CRF and all source documents / data, including progress notes, copies of laboratory and medical test results, which must always be available for review by the CRA, auditor and regulatory inspector (e.g. FDA). They may review all CRFs and informed consents. The accuracy of the data will be verified by direct comparison with the source documents described in Section 8.3.1. The contracting entity or delegate will also monitor compliance with the protocol and GCP.

8.3.3 Storage period of records

Study site(s):

The study site(s) must retain the source and essential documents (including ISF) according to contract or the local requirements valid at the time of the end of the study (whatever is longer).

Contracting entity:

The contracting entity must retain the essential documents according to the contracting entity's SOPs.

8.4 EXPEDITED REPORTING OF ADVERSE EVENTS

BI is responsible to fulfil their legal and regulatory reporting obligation in accordance with regulatory requirements.

Proprietary confidential information © 2022 Boehringer Ingelheim International GmbH or one or more of its affiliated companies

8.5 STATEMENT OF CONFIDENTIALITY AND PATIENT PRIVACY

Data protection and data security measures are implemented for the collection, storage and processing of patient data in accordance with the principles 7 and 12 of the WHO GCP handbook.

To ensure confidentiality of records and personal data, only pseudonymised data will be transferred to the contracting entity by using a patient identification number instead of the patient's name. The code is only available at the site and must not be forwarded to the contracting entity. In case patient's records will be forwarded e.g. for SAE processing or adjudication committees, personal data that can identify the patient will be redacted by the site prior to forwarding. Access to the patient files and clinical data is strictly limited: personalised treatment data may be given to the patient's welfare. Data generated at the site as a result of the study need to be available for inspection on request by the participating physicians, the contracting entity's representatives, by the IRB / IEC and the regulatory authorities.

A potential data security breach will be assessed regarding the implications for rights and privacy of the affected person(s). Immediate actions as well as corrective and preventive actions will be implemented. Respective regulatory authorities, IRBs / IECs and patients will be informed as appropriate.

8.6 STUDY MILESTONES

The **start of the study** is defined as the date when the first patient in the whole study signs informed consent.

The end of the study is defined as the date of the last visit of the last patient in the whole study ("Last Patient Completed"). **Early termination of the study** is defined as the premature termination of the study due to any reason before the end of the study as specified in this protocol.

Temporary halt of the study is defined as any unplanned interruption of the study by the contracting entity with the intention to resume it.

Suspension of the study is defined as an interruption of the study based on a Health Authority request.

16 Sep 2022

Protocol

Page 47 of 71

Proprietary confidential information © 2022 Boehringer Ingelheim International GmbH or one or more of its affiliated companies

8.7 ADMINISTRATIVE STRUCTURE OF THE STUDY

The study is sponsored by Boehringer Ingelheim (BI).

A Coordinating Investigator is responsible to coordinate investigators at the different sites participating in this study. Tasks and responsibilities are defined in a contract.

Relevant documentation on the participating (Principal) Investigators (e.g. their curricula vitae) will be filed in the ISF.

BI has appointed a Clinical Trial Leader responsible for coordinating all required activities, in order to

- manage the study in accordance with applicable regulations and internal SOPs,
- direct the study team in the preparation, conduct, and reporting of the study,
- ensure appropriate training and information of Clinical Trial Managers (CT Managers), Clinical Research Associates (CRAs), and investigators of participating countries.

In the participating countries the study will be performed by the respective local or regional BI-organisation (Operating Unit, OPU) in accordance with applicable regulations and BI SOPs.

Data Management and Statistical Evaluation will be done by BI according to BI SOPs.

Tasks and functions assigned in order to organise, manage, and evaluate the study are defined according to BI SOPs. A list of responsible persons and relevant local information can be found in the ISF.

A central laboratory service will be used in this study. Details will be provided in the Central Laboratory Manual, available in the ISF.

Page 48 of 71

Proprietary confidential information © 2022 Boehringer Ingelheim International GmbH or one or more of its affiliated companies

9. **REFERENCES**

9.2 UNPUBLISHED REFERENCES

Not applicable

Page 50 of 71

Proprietary confidential information © 2022 Boehringer Ingelheim International GmbH or one or more of its affiliated companies

10. APPENDICES

10.1 INSTRUCTIONS FOR USE

Patient will be provided with User Manuals for the study devices

Page 51 of 71

 406431-01
 Protocol
 Page 52 of 71

 Proprietary confidential information © 2022 Boehringer Ingelheim International GmbH or one or more of its affiliated companies
 Proprietary Confidential information © 2022 Boehringer Ingelheim International GmbH or one or more of its affiliated companies

 406431-01
 Protocol
 Page 53 of 71

 Proprietary confidential information © 2022 Boehringer Ingelheim International GmbH or one or more of its affiliated companies
 Proprietary Confidential information © 2022 Boehringer Ingelheim International GmbH or one or more of its affiliated companies

Page 54 of 71

Page 55 of 71

Page 57 of 71

 406431-01
 Protocol
 Page 58 of 71

 Proprietary confidential information © 2022 Boehringer Ingelheim International GmbH or one or more of its affiliated companies
 Proprietary Confidential information © 2022 Boehringer Ingelheim International GmbH or one or more of its affiliated companies

Page 59 of 71

Page 60 of 71

Page 61 of 71

Page 62 of 71

Page 63 of 71

Page 64 of 71

 406431-01
 Protocol
 Page 65 of 71

 Proprietary confidential information © 2022 Boehringer Ingelheim International GmbH or one or more of its affiliated companies
 Proprietary Confidential information © 2022 Boehringer Ingelheim International GmbH or one or more of its affiliated companies

 9406431-01
 Protocol
 Page 66 of 71

 Proprietary confidential information © 2022 Boehringer Ingelheim International GmbH or one or more of its affiliated companies
 Proprietary Confidential information © 2022 Boehringer Ingelheim International GmbH or one or more of its affiliated companies

 406431-01
 Protocol
 Page 67 of 71

 Proprietary confidential information © 2022 Boehringer Ingelheim International GmbH or one or more of its affiliated companies
 Page 67 of 71

16 Sep 2022

Protocol

Page 68 of 71

Proprietary confidential information © 2022 Boehringer Ingelheim International GmbH or one or more of its affiliated companies

10.4 PATIENT SURVEY

Patient Feedback Survey – 1490-0005

Dear Participant,

Thank you for participating in Boehringer Ingelheim study 1490-0005. We would like your feedback on your experience in using **remote technologies** in this study. Your feedback (all optional) will not affect your study participation in any way.

Please mark the box that best represents how you feel about your recent use of the

The completion of this survey should take you approximately 10 minutes.

cough monitor system for each of the statements below.

Experience with the cough monitor system

-						
		Strongly				Strongly
Sto	itements:	Agree	Agree	Neutral	Disagree	Disagree
1)	The OVERALL EXPERIENCE with the cough monitor system was good.					
2)	The INSTRUCTIONS for the cough monitor system (written patient guide) were easy to understand.					
3)	It was easy to SET UP the cough monitor system at home (including finding the right position for placement of the Biosensor on the chest, attachment with adhesive, starting the sensor)					
4)	Wearing the Biosensor during DAYTIME was comfortable.					
5)	Wearing the Contractor Biosensor while ASLEEP was comfortable.					
6)	I was able to REMOVE the Biosensor including adhesive from my chest without any difficulties.					
7)	Using the Sector Biosensor CHARGING STATION was easy.					
8)	UPLOADING the cough monitor results via the app was easy.					

9) Was there any INFORMATION MISSING in the instructions (written patient guide)?

□ No □ Yes, please specify

- 10) What did you LIKE about the cough monitor system (including but not limited to instructions, biosensor patch, charging station, measurements, uploading results, app)? Comment
- 11) What did you DISLIKE about the cough monitor system (including but not limited to instructions, biosensor patch, charging station, measurements, uploading results, app)? Comment

7

Page 1 of 3

Page 69 of 71

Proprietary confidential information © 2022 Boehringer Ingelheim International GmbH or one or more of its affiliated companies

Boehringer Ingelheim

Patient Feedback Survey - 1490-0005

12) What could be changed to IMPROVE your experience with the cough monitor system? Comment

13) Is there any OTHER feedback you would like to share about the cough monitor system? Comment ______

Experience with the video call assisted home spirometry

Please mark the box that best represents how you feel about your recent use of the video call assisted home spirometry for each of the statements below.

	Strongly				Strongly
Statements:	Agree	Agree	Neutral	Disagree	Disagree
-0			×		
-12			-		
-16					
-8					
	1				

Page 2 of 3

Page 70 of 71

Proprietary confidential information © 2022 Boehringer Ingelheim International GmbH or one or more of its affiliated companies

Experience with the Virtual Visits

Please mark the box that best represents how you feel about your recent use of the **virtual visit function** for each of the statements below.

Statements:	Strongly Agree	Agree	Neutral	Disagree	Strongly Disagree
	a	¥ 75		9	

Please provide any further comments about your experience in the comment box.

Thank you!

Version + n

Page 3 of 3

16 Sep 2022

Protocol

Page 71 of 71

Proprietary confidential information © 2022 Boehringer Ingelheim International GmbH or one or more of its affiliated companies

2. LIST OF ABBREVIATIONS

Term	Definition / description
ANOVA	Analysis of variance
BMI	Body Mass Index
CC	Couth Count
CfB	Change from baseline
CTP	Clinical Trial Protocol
CV	Coefficient of Variation
ES	Enrolled Set
FAS	Full Analysis Set
ICH	International Conference on Harmonisation
LOCF	Last Observation Carried Forward
OC	Observed Case
OR	Original Results
TS	Treated Set
TSAP	Trial Statistical Analysis Plan

3. INTRODUCTION

As per ICH E9, the purpose of this document is to provide a more technical and detailed elaboration of the principal features of the analysis described in the protocol, and to include detailed procedures for executing the statistical analysis of the primary and secondary variables and other data.

This TSAP assumes familiarity with the Clinical Trial Protocol (CTP), including Protocol Amendments. In particular, the TSAP is based on the planned analysis specification as written in CTP Section 7 "Statistical Methods and Determination of Sample Size". Therefore, TSAP readers may consult the CTP for more background information on the study, e.g., on study objectives, study design and population, treatments, definition of measurements and variables, planning of sample size, randomization."

SAS[®] Version 9.4 will be used for all analyses.

4. CHANGES IN THE PLANNED ANALYSIS OF THE STUDY

For the endpoint "Cough frequency and number of cough bouts at each of the activity levels (exertion): stationary/low, medium/high", activity levels will be categorized as:

- Low activity
- Medium activity
- High activity

"Stationary" activity represents non-wear time.

Only inspiratory crackles will be summarized for the endpoint "Lung sound events (potentially including, but not limited to, inspiratory crackles)

5. **ENDPOINTS(S)**

5.1 **PRIMARY ENDPOINT(S)**

The primary endpoints as stated in the CTP are: Cough count per hour (CC/hr) measured over a 24-hour period at baseline visit, Week 4(V4), Week 8(V5), Week 12 (V6).

Note that these endpoints are the average CC/hour at each of the 4 visits.

5.2 SECONDARY ENDPOINT(S)

5.2.1 Key secondary endpoint(s)

Not applicable, there are no defined key secondary endpoints

5.2.2 Secondary endpoint(s)

Cough related endpoints:

• Change from baseline in CC/hr at Week 4, Week 8, Week 12.

Spirometry related endpoints:

- FVC (mL) at baseline
- FVC (mL) at Week 12
- Change from baseline in FVC (mL) at Week 12

Study feasibility endpoints:

- Feasibility of remote cough data capture (defined as % of analysable data per 24-hour recording)
- Feasibility of hybrid study design (successful completion of all elements of remote visit)

Boehringer Ingelheim

 TSAP for BI Trial No: 1490-0005
 Page 8 of 27

 Proprietary confidential information © 2024 Boehringer Ingelheim International GmbH or one or more of its affiliated companies

6. GENERAL ANALYSIS DEFINITIONS

6.1 **TREATMENT(S)**

Not applicable, patients did not receive treatment in this trial

6.2 IMPORTANT PROTOCOL DEVIATIONS

Handling of iPDs in analysis is included in the DV domain specifications and stored within the TMF in EDMS. Other relevant documentation of details related to iPDs will be included in the CQM minutes

6.3 SUBJECT SETS ANALYSED

The subject analysis set used for reporting is defined as:

Entered Set (ES): those patients who were entered into the study.

The ES will be used for all types of endpoints including:

- Demographic/baseline endpoints
- Primary endpoints
- Secondary endpoints
- Safety
- •

6.5 **POOLING OF CENTRES**

There will be no statistical model specified for the primary analysis, therefore pooling of centers is not applicable.

6.6 HANDLING OF MISSING DATA AND OUTLIERS

The following approaches will be applied in this trial:

- The original results (OR) approach implies the presentation of data exactly as observed (not using time windows as described in Section 6.7 and not setting values to missing). OR analysis will be performed on parameters and endpoints for which it is not meaningful to apply any imputation rule for the replacement of missing values.
- Observed cases (OC) approach will include all collected data, without imputation for any missing data after applying the time windows as described in Section 6.7

Missing or incomplete AE dates are imputed according to BI standards.

Other partial start and stop dates, for example, concomitant medications, non-drug therapies, and IPF diagnoses will be imputed to enable subsequent calculation (but not for display) by the following approach:

- If the day of the end date is missing, then the end date is set to last day of the month (or to the patient's end of study participation from End of Study eCRF. if it is earlier than the last day of the month).
- If the day and month of the end date are missing then the end date is set to 31st of December of the year (or to the patient's end of study participation from End of Study eCRF, if it is earlier than the 31st of December of the year).

Boehringer Ingelheim TSAP for BI Trial No: 1490-0005

Proprietary confidential information © 2024 Boehringer Ingelheim International GmbH or one or more of its affiliated companies

- If the day of the start date is missing the start date is set to first day of the month.
- If the day and month of the start date are missing then the start date is set to 1st January of the year.
- All other cases need to be assessed by the trial team on an individual basis, using the above points as guidance.

6.7 BASELINE, TIME WINDOWS AND CALCULATED VISITS

In general baseline is defined as measurements collected at the Baseline visit. For the first of the value at the Baseline visit is missing the value at the Screening visit will be used.

As this is a low-interventional trial without treatment or other intervention for cough, in cases where the first cough recording or in-office spirometry occurred after the Baseline visit (Visit 2) then the start date of the first cough recoding or first in-office spirometry visit will be considered the Baseline measurement and the time windows below will be applied to the subsequent visits using the respective baseline date as day 1.

Table 6.7: 1Time windows for assignment of visits for	statistical analysis
---	----------------------

		Time windows (days)			
		Planned day	Window		
Visit			(relative to		
name	Visit label		planned day)	Start (inclusive)	End (inclusive)
V1	Screening	-7	n/a		
V2	Baseline	1	n/a	-7	1
V3	Day 3 ^a	3	-1/+13	2	16
V4	Week 4 ^a	29	-12/[contact]
V5	Week 8 ^a	57	-13/[contact]
V6	Day 82 ^a	83	-13/na	71	One day before
	-				last visit (in-
					office)
V7	Week 12/EoS	85	na/na	Date of last visit (in-	Last visit date
				office)	recorded

^a Remote visit

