2.1 MAIN OBJECTIVES, PRIMARY AND SECONDARY ENDPOINTS

2.1.1 Main objectives

The primary objective of this study is to objectively describe cough frequency, utilizing four 24-hour cough recordings over 12 weeks in a cohort of subjects with Non IPF Pulmonary Fibrosis or IPF using the cough monitor.

The secondary objectives for this study are:

- Assess the relationship between objective cough frequency and FVC (mL)
- Assess feasibility of patient performed remote cough data upload
- Assess feasibility of hybrid study design (% successful completion of remote visits)

2.1.2 **Primary endpoint(s)**

Primary Endpoints: Cough count per hour (CC/hr) measured over a 24-hour period at baseline visit, Week 4(V4), Week 8(V5), Week 12 (V6).

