7.4 PRIMARY ENDPOINT(S)

7.4.1 **Primary analysis of the primary endpoint(s)**

CTP Section 7.2.3: The cough count (CC) frequency, measured over 4 24-hour recordings in 12 weeks will be analysed as CC/hour and will be log-transformed for data summaries. On each day for which cough monitoring is completed, the log-transformed cough count is calculated as:

Log-transformed cough count = $log \frac{Number of coughs}{Length of readable recorded time (hours)}$

Cough count for each visit will be reported descriptively. Summary statistics will be tabulated on original scale of CC/hr as well as the geometric mean and 95% confidence intervals after back-transforming the summarized log transformed data.

Summary measurements and individual values of CC/hr over time will also be presented graphically.

Descriptive statistics, including the coefficient of variation (CV), for cough count/hour will be tabulated by visit using the original scale and for the log (natural) transformed values. In cases where 0 coughs are observed during a recording interval (e.g. night time, low activity duration, or over the 24 hour recording period), 0.1/hr will replace 0 in order to allow for the log transformation. Geometric means, coefficients of variation and 95% CIs be presented as well. For these, the summary measures using the log-transformed values will be calculated then back-transformed to the original scale.

Boehringer Ingelheim TSAP for BI Trial No: 1490-0005

Proprietary confidential information © 2024 Boehringer Ingelheim International GmbH or one or more of its affiliated companies

Plots of the geometric means and geometric mean ratios over time will be produced. Individual time profiles for CC/hr will also be presented graphically.

The primary endpoints will be summarized in the same fashion as described above by each subgroup level listed in Section 6.4.

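### Counting the SAP 6.7 windows from a late first recording can move on-schedule V4 and V6 cough values off their protocol labels, and Week 12/EoS FVC has no earliest day

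*SAP*

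**What the plan says.** The primary endpoint in Protocol 2.1.2 is CC/hr "measured over a 24-hour period at baseline visit, Week 4(V4), Week 8(V5), Week 12 (V6"). SAP 5.1 adds: "Note that these endpoints are the average CC/hour at each of the 4 visits". SAP 7.4.1 then states: "Cough count for each visit will be reported descriptively".

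Protocol 6.1 times V4 and V5 from the enrolment/baseline visit and puts V6 on the 82nd day. It does not move them when the first recording is late.

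Under SAP 6.7, when the first cough recording or first in-office spirometry takes place after Visit 2, "the start date of the first cough recoding or first in-office spirometry visit will be considered the Baseline measurement". The time windows "will be applied to the subsequent visits using the respective baseline date as day 1". No latest day is set for such a Baseline.

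In SAP Table 6.7: 1, V3, V4 and V5 have day-numbered windows. V6 has a numeric start, and its end is given as "One day before" the last in-office visit. V7, labelled Week 12/EoS, has window na/na and starts on the date of the last in-office visit.

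SAP 6.6 defines two approaches. Original results (OR) present data "not using time windows as described in" Section 6.7. Observed cases (OC) use the data "after applying the time windows as described in Section 6.7". The readable text does not assign CC/hr to either.

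**The concern.** The by-visit CC/hr summary needs no baseline. A V4 recording made on its protocol date is a Week 4 value whenever the first recording took place. If the windows move with a late first recording while the visits keep their dates, a valid value can be filed under another visit, or under V3, which has no cough endpoint. The adjusted model in SAP 7.5.2 uses visit as a factor, so a wrong label would carry into the geometric mean ratios.

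The FVC side is a separate gap. Week 12 FVC and its change are secondary endpoints, and four of the five planned correlations use one or the other. With no earliest day in the V7 row, an early last in-office value would enter all of these as Week 12.

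**Working it through.** **Inputs.** From SAP Table 6.7: 1: V3 planned Day 3, offsets -1/+13, printed 2 to 16; V4 planned Day 29, lower offset -12; V5 planned Day 57, lower offset -13; V6 planned Day 83, lower offset -13, printed start 71; V7 planned Day 85, na/na. The printed V4 and V5 limits are not readable in the public text, so their starts are derived. From the protocol flow chart: V4, V5, V6 and V7 on Days 28, 56, 82 and 84, with +/- 5 days for V4, V5 and V7 and -2 days for V6. The delay of the first recording is an assumption, because neither document gives one.

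**Step 1: reproduce the table** (limit = planned day + offset).
- V3: 3 - 1 = 2 and 3 + 13 = 16, as printed.
- V4 start: 29 - 12 = 17, the day after V3 ends. V5 start: 57 - 13 = 44.
- V6 start: 83 - 13 = 70. The table prints 71, which would need an offset of -12. The row contradicts itself by one day.

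**Step 2: apply the re-dating** (re-dated day = study day - delay, Visit 2 = Day 1).

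| Visit days used | Delay | V4 | V5 | V6 |
|---|---|---|---|---|
| SAP planned (29, 57, 83) | 12 | 17 | 45 | 71 |
| SAP planned | 13 | 16 | 44 | 70 |
| SAP planned | 14 | 15 | 43 | 69 |
| Flow chart (28, 56, 82) | 11 | 17 | 45 | 71 |
| Flow chart | 12 | 16 | 44 | 70 |
| Flow chart | 13 | 15 | 43 | 69 |

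On SAP planned days all three visits keep their labels up to a 12-day delay. At 13 days V4 falls in the V3 window (2 to 16) and V6 falls before the printed 71. On flow-chart days both happen one day sooner. If the V6 start were 70, V6 would leave at 14 days (83 - 14 = 69) or 13 days (82 - 13 = 69). V5 falls below its derived start of 44 at 14 days (SAP days) or 13 days (flow chart).

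**Step 3: visits inside the protocol tolerance** (SAP days). V4 between Days 24 and 34 enters the V3 window at delays between 8 days (24 - 8 = 16) and 18 days (34 - 18 = 16). V6 on Day 81 leaves at 11 days against the printed start (81 - 11 = 70).

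**Step 4: V4 is the first recording.** The delay is 28 days, so V5 becomes 57 - 28 = Day 29 and V6 becomes 83 - 28 = Day 55. No Week 12 CC/hr remains for that patient.

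**Step 5: FVC.** The protocol puts V7 at 84 +/- 5, that is Days 79 to 89. The SAP row gives no numeric lower limit to compare with this.

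**Step 6: size.** One patient is 1/50 = 2% of a 50-patient summary. An assumed 0 to 3 patients would be 0% to 3/50 = 6%.

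**The case against.** The strongest reply is that the cough effect is conditional. It arises only if OC windows are applied to CC/hr, and SAP 6.6 also offers an approach without windows. That stands. Section 6.7 does name cough recordings when it ties the windows to the new Day 1, so applying them is the natural reading, but the plan should say so.

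The trigger also looks rare. Under Protocol 6.1 the first recording is started with supervision at Visit 2, and the sponsor may decide to reschedule a missed visit. That stands as well, although the SAP wrote this rule because it foresaw late first recordings.

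Re-dating has a stated reason: there is no treatment or other cough intervention. The SAP also tabulates changes alongside the primary endpoint, so one label per recording is tidy. For change from baseline this is sound. It does not carry over to a by-visit summary that uses no baseline.

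Two stronger readings are tempting and are not supported:
- **That V6 values are deleted.** The V5 end is not readable. V3 and V4 are adjacent, and a V5 end of 70 would meet the V6 start of 71, so relabelling as Week 8 is at least as likely. Neither outcome can be shown.
- **That the V6 window collapses when there is no in-office EoS visit.** Read literally, the last in-office visit would be Visit 2 and the window would end on Day 1 - 1 = 0. The phrase most plausibly means V7, so this needs only a clarifying line.

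On FVC, in-office spirometry is scheduled only at V2 and V7, no early-termination visit is visible, and the label itself includes EoS. Early values should be few, but nothing in the SAP separates them from Week 12.

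**Conclusion.** The point holds in a limited form. Where the windows are applied to CC/hr, an on-schedule V4 or V6 can leave its protocol label from a delay of 13 days (SAP planned days) or 12 days (flow-chart days), and from 8 days for the earliest permitted V4. V6 is then relabelled or dropped, depending on the V5 end. Two parts do not depend on a late first recording: Week 12/EoS FVC has no earliest day, and the V6 row gives 70 by its offset and 71 in print.

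This rests on OC being used for CC/hr, on later visits staying timed from Visit 2, and on V4 and V5 starts derived from their offsets. The number of affected patients cannot be computed from the documents and is probably low.

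A reader might infer that the study's conclusions are put at risk. The documents do not support that: Protocol 7.1 plans no confirmatory testing, and data listings and individual profiles will still show each patient's values. The harm is a mislabelled or missing visit value, which makes this a minor to moderate correction.

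**What to change.** - **CC/hr by visit:** assign V4, V5 and V6 with the existing windows counted from Visit 2 for every patient, and state that OC applies.
- **Change from baseline:** keep the late first recording as Baseline, keep the SAP's own window widths counted from it, and show days since baseline. Do not impose a narrower tolerance on late-Baseline patients only. With +/- 5 days, for example, a 6-day delay puts the changes at 22, 50 and 76 days, each 6 days short of 28, 56 and 82, and all three would lose labels that the SAP windows keep (re-dated Days 23, 51 and 77, taking adjacent windows).
- **FVC:** count an in-office value as Week 12 only from a stated earliest day, for example the V6 window start, and tabulate earlier EoS values separately.
- **V6 row:** reconcile the -13 offset with the start of 71, and state that the window ends at last contact when no in-office EoS visit takes place.

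The cost is SAP wording and a little programming, with no change to data collection. A few early EoS values would leave the Week 12 FVC summary. For late-Baseline patients the visit label and the change label may differ, so the SAP should say which one the adjusted model uses. A first recording made on Day 17 or later would itself fall in the Week 4 window counted from Visit 2, so the SAP should also say which label it takes.
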